4.3.3. Patient Training Study Design (Phase III)

Immediately after consent, patients will be administered a baseline self-report survey. The table on the following page shows the anticipated schedule of self-report measures to be completed by patients participating in the Patient Training Study (Phase III) as well as the number of items and estimated length of time needed to complete the survey at both time points. Assessments will primarily be conducted using RedCap forms, which are HIPAA compliant and convenient for participants, particularly for baseline (T1) and 2-month follow-up data (T3), whereas post-intervention (T2) data will generally be collected primarily in-person in clinic immediately following the clinic visit which was audio recorded. However, survey data may be administered using paper-based forms in the case that patients are unable or unwilling to complete online surveys and can be collected either through the mail or in person; telephone collection may also be used if needed to facilitate efficient and timely gathering of follow-up data. Medical data will be collected from medical records and include: stage of disease, dates of diagnosis, surgeries, and treatments, and current and past breast cancer treatments.

We will use block randomization to randomize patients 1:1 to either condition with stratification by (a) metastatic disease (Stage IV) vs. non-metastatic disease (anything other than Stage IV) and (b) education (less than or equal to 12 years of education, i.e., a high school diploma) vs. any more than a high school education (equivalent to more than 12 years of education) to assign 64 patients to the Skills-based training plus menopausal and sexual health resources and 64 patients to the Control condition (menopausal and sexual health resources only).

The patient training intervention will consist of multiple aspects such as PowerPoint slides with voiceover and audio or video clips, along with a workbook. The materials will be sent to participants using a RedCap link, after consent, completion of baseline surveys, and randomization. Patients will be able to complete the intervention either at home using their own computer or other device, or in-person in a private location at Fox Chase, either in advance of their clinic visit or the day of their clinic visit. This flexibility will allow patients without computer access to participate, while still maintaining a consistent time frame in which the assessments and intervention will be delivered.

Patient Training Study (Phase III) Patient Self-Report Measures					
Measure	# Items	Minutes to Complete	Baseline	Post-Training	2-Month Follow-up
Demographics	7	5	X	-	-
Patient-Provider Communication Self-Efficacy (PEPPI-5)	5	3	X	X	X
Beliefs (Self-efficacy/Outcome expectations) ^{67,75}	18	5	X	X	X
Barriers to discussing sexual health	13	4	X	-	X
Self-Report of Communication During Patient Visit	20	10	-	X	-
Hospital Anxiety and Depression Scale (HADS)	27	10	X	-	X
Dyadic Adjustment (DAS-4) ⁷⁶	4	2	X	-	X
Quality of Life (FACT-B Brief) ⁷⁷	23	10	X	-	X
HRQOL Items	10	4	-	X	-
PROMIS SexFS Brief Profile Version 2 (Female) ⁷⁸	14	5	X	-	X
Information/Help-Seeking ⁷⁹	3	2	X	-	X
Therapeutic Aids ⁸⁰	3	3	X	-	X
Satisfaction with Interaction with Provider ⁸¹	4	2	-	X	-
Program Evaluation (Skills-Based Training patients only)	20	10	-	X	-
Resources Evaluation	6	3	-	X	-
Totals					
- Baseline (T1)	117	49			
- Post-Training (T2)	77	37			
- 2-Month Follow-up (T3)	126	44			

Skills-Based Training. Details of this intervention have been informed by the results from both Phases I and II. Using a social cognitive framework,⁸² the 20-minute intervention (Starting the Conversation) consists of an informational and skills-based video and accompanying workbook. This intervention is designed to increase self-efficacy and outcome expectancies for communicating with providers about menopausal and sexual health, reduce barriers to communication, and provide basic training in skills for communicating with providers about menopausal and sexual health, including prioritizing concerns, tips for effective communication, communication practice, and self-feedback. Planned communication content and structure are influenced by other skills-based patient-focused training interventions in cancer^{57,83}, results from Phases I and II of our study (e.g., patient cognitive interviews, data from clinic dialogue

suggesting that patients infrequently ask questions during clinic visits), current research on menopausal and sexual side effects of breast cancer treatment, and the input of study team members who have expertise in patient-provider communication ([name]), behavioral patient interventions ([name], [name], [name]), breast cancer ([name]), and menopausal and sexual health for women with cancer ([name], [name]). In addition to viewing the module, participants will be sent a workbook to go along with the video module. Patients in the Skills-Based Training condition will also receive resources on menopausal and sexual health for breast cancer survivors, in the form of a list of informational resources (e.g., websites, Fox Chase resources or clinics). Control Condition. Patients randomized to the Control group will receive the same list of menopausal and sexual health resource guide as the patients in the Skills-Based Training group, but will not be asked to participate in the Starting the Conversation intervention. After completion of all study measures and the recording of their clinic visit, interested Control group patients will be offered the opportunity to participate in Starting the Conversation (i.e., to watch the video and use the workbook).

The patient's first clinic appointment following her participation in the patient training program with the post-training provider will be audio recorded using the methodology described earlier for recording of the provider baseline visits.

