Study Design: First, we will identify barriers and preferences for patient-provider communication about sexual concerns and practical and preferred methods for administering the provider and patient training programs. Using qualitative interviews and focus groups with both providers and patients, we will design provider and patient training programs and refine them through expert team review and mock trainings and tailor an intimacy enhancement intervention for breast cancer survivors. Second, we will test the feasibility and acceptability of the training program in a new group of 6-8 providers, and examine change in providers' beliefs up to 6-months post-training. We expect that the frequency and quality of provider communication behaviors relating to sexuality will increase following training through coding pre- and post-training audio recorded clinic dialogue and/or through patient self-reports of communication that occurred during the clinic visits. Third, we will randomize 144 breast cancer patients with sexual concerns to a brief Skills-Based Training plus menopausal and sexual health resources or a Control condition (menopausal and sexual health resources only) prior to a routine clinic visit with a trained provider. We expect that the Skills-based training program will be feasible and acceptable and that patients will exhibit greater increases in pre- to post-training beliefs at 2-month follow-up compared with patients in the Informational Control condition. Through coding audio recorded clinic visits immediately following training, we expect that patients receiving the Skills-based training will ask more questions and express more concerns pertaining to sexuality than control patients. In additional analyses, we will examine the impact of training on psychological health, sexual function and activity, and QOL at 2-month follow-up. In a separate forthcoming study, we will pilot test the newly tailored Intimacy Enhancement intervention which will follow from the information gathered in the exploratory aim.

Significance: The lack of discussion about sexual concerns relative to the severity and importance of these concerns to women with breast cancer make this issue a major priority. The programs we develop will address an important, undertreated area of concern for breast cancer patients. Addressing breast cancer patients' sexual concerns can enhance patient-centered care and improve patients' intimate relationships and QOL.

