2.0 Objectives

2.1 Primary Objectives

2.1.1. Primary Objective I.

To develop, refine and pilot test a provider training program to enhance communication about breast cancer-related sexual concerns. First, using qualitative interviews with 12 breast cancer providers, we will design a program and then refine it through expert review and mock trainings. Through these interviews, we will identify provider barriers and preferences for communicating with patients about sexual concerns and practical and preferred methods for implementing training. Next, we will pilot test the training program in 6-8 new breast cancer providers. Outcomes will include feasibility, acceptability, and change in providers' beliefs from pre- to post-training and at 1- and 6-month follow-up. Finally, we will examine provider communication behaviors coded from pre- and post-training audio recorded clinic visits (i.e., asking questions about sexuality, offering information about sexual concerns) and/or through patient self-reports of communication that occurred during the clinic visits.

2.1.2. Primary Objective II.

To develop, and refine, and evaluate a patient training program to enhance communication about breast cancer-related menopausal and sexual concerns. First, using qualitative focus groups/interviews with 24 breast cancer survivors, we will design a Skills-based training program and will refine this program through expert review and mock trainings with 6 new breast cancer survivors. Through these focus groups, we will identify patient barriers and preferences for communicating with providers about sexual concerns and practical and preferred methods for implementing training. Next, we will randomize 144 patients to either a Skills-based training plus menopausal and sexual health resources prior to their clinic visit with a previously trained provider or a control condition (menopausal and sexual health resources only) and examine effects of the intervention on patient communication beliefs. Finally, we will examine patient communication behaviors coded from audio recorded clinic visits following the training (e.g., asking about sexual concerns, expressing a sexual concern).

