For participating in Phase I (Qualitative Study) providers will receive \$75. Providers in Phase II (Provider Training) will receive \$500 to compensate them for the substantial time and efforts involved in allowing us to assess communication in multiple patient visits, participate in the provider training program, and complete follow-up materials. They will receive this compensation split between three time points, in order to allow for a more timely repayment of their efforts: providers will receive \$200 at the time of completion of post-intervention surveys, which will occur at the end of the provider training, another \$200 once all follow-up Phase II clinic encounters have been assessed (and recorded, if possible), and a final \$100 at the time of completion of the 6-month post-training survey. Fellows, nurses, students, or other third parties that are recorded as part of the clinic visit assessments will not be compensated. Providers participating in Phase III will be compensated \$25 after the audio recording of their first patient and an additional \$25 after the audio recording of their final patient (i.e., at the study conclusion), for a total of \$50. Compensation will be provided in the form of gift cards or check.

Number of subjects per year projected at FCCC	Total target accrual	Number of subjects nationally or internationally (if applicable)	Number of subjects at collaborating institutions (if applicable)
Up to: 59*	339	N/A	29*

* The yearly rate will differ by study phase. In Year 1, we anticipate enrolling up to 59 Fox Chase or Temple patient participants (though some participants may be from other outside sites) and 4 oncology fellows for Phase I; 12 Phase I providers will be recruited from Temple or other sites. In Years 2-5, we plan to enroll 256 Fox Chase patients, and 5-8 Fox Chase providers. Overall, a lower accrual goal is 305, a total target accrual goal is 339, and an upper accrual goal for Fox Chase is 349. We may also recruit Temple providers or other outside providers for Phase II if we are unable to recruit a sufficient number of internal clinicians for this phase of the study. If we are able to recruit a Temple or outside provider, then the number of target patients may change slightly for Fox Chase, because we will be recruiting about 16 patients per provider from outside Fox Chase.

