4.1.2. Recruitment and Reimbursement of Patient Participants

Across all study phases, a target of 315 patients will participate in the study: 30 participants in Phase I (Qualitative Study); 24 focus group participants, 6 mock training participants); 168 patients in Phase II (Provider Training Study); and 144 in Phase III (Patient Training Study); 24 patients in the exploratory focus groups, and 5 in the cognitive interviews.

Candidates for Phase I (qualitative study/mock training) and for the exploratory focus groups will be recruited primarily through advertisements both internally via clinics at Fox Chase/Temple and externally via established community partners and other sites, telephone, and in-person at clinic at Fox Chase or Temple after identification through providers' schedules, or after identification through the Fox Chase Cancer Registry, using a study introductory letter (see supplemental materials). For patients identified through the Registry, patient lists will be approved by the patients' physician prior to sending the introductory letter. Given an approximately 20% no-show rate for the qualitative focus groups, we will recruit and schedule between 5 to 8 patients for focus groups, assuming that several candidates will not

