Candidates for Phase II (Provider Training Study) will be identified in advance through providers’ schedules and will be recruited primarily in-person in the clinic or through contact with a study letter prior to their planned visit. Pre-screening by the study team will identify candidates who are eligible and the patient’s provider will give final approval for approaching the patient. No separate screening is necessary. Candidates will have the opportunity to opt out either in-person, or over the telephone if contacted through the study letter in advance of their visit. For Phase III (Patient Training Study; N=144), recruitment will primarily be conducted through contact with a study letter for pre-screened patients approved by provider for contact in advance (generally 2-4 weeks) of a scheduled visit with a trained provider. Patients will have the opportunity to opt out as described above. A telephone screening call by the study team will confirm patient eligibility and assess accessibility of computer/devices, include a brief assessment of socio-demographic and medical characteristics, and health-related quality of life (e.g., level of sexual concerns, pain, fatigue), and include a detailed discussion of the study procedures. Advertisements may also be used for these phases, as needed.

For participating in Phase I (focus group/interview or mock training) or in the exploratory focus groups or cognitive interviews, participants will receive \$75. Patients participating in Phase II (Provider Training Study) will receive \$10 in compensation for completing the self-report materials and allowing us to assess communication during their clinic visit. For participating in Phase III, patients will receive \$60 for completing the self-report materials. Compensation will be provided in the form of gift cards, which will be given to patients at the time of completion of each of the 3 assessments (\$20 each; \$60 total).

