13.3.4. Sample Size Calculations

The sample size calculations are based on the primary belief outcomes. Based on prior literature,⁹⁰ we assume a standard effect size of .60 on the outcome of patient beliefs. We therefore aim to accrue up to 144 patients (72 per arm) in order to collect an estimated 128 audio recordings (64 per arm) to have 80% power to detect a standard effect of 0.5, with 5% two-sided type-I error.

Other primary outcomes include A) the proportion of visits where the patient asks a question, and B) the proportion of visits where the patient brings up sexual health. Based on preliminary data, we expect these proportions to be low in the control arm (15% and 22%, respectively). We also anticipate that 70% of visits will be informative for outcome B (only visits where the physician does NOT bring up sexual health to be included). Therefore, with sample size of 128 audio recordings, we will have 80% power with 5% 2-sided type-I error to detect rates of 38% for outcome A in the intervention arm versus 15% in the control arm (calculations using Fisher's exact test). For outcome B, assuming 45 informative visits per arm, we will have sufficient power to detect rates of 52% in the intervention arm versus 22% in the control arm.

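### Section 4.3.3 randomises 64 patients per arm, the number of recordings that 13.3.4 expects from 72 per arm; separately, the accrual totals fall 56 short of their listed parts

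*Combined protocol and SAP*

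**What the plan says.** **Phase III size.** Section 4.3.3 describes stratified 1:1 block randomisation "to assign 64 patients to the Skills-based training plus menopausal and sexual health resources and 64 patients to the Control condition", that is, 128 patients. Everywhere else the number is 144:

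- Section 1.0, Study Design: "we will randomize 144 breast cancer patients".
- Section 2.1.2: "Next, we will randomize 144 patients to either a Skills-based training plus menopausal and sexual health resources".
- Section 4.1.2, in the patient target: "168 patients in Phase II (Provider Training Study); and 144 in Phase III (Patient Training Study".
- Section 4.1.2, on recruitment: "For Phase III (Patient Training Study; N=144".
- Section 13.3.4: "We therefore aim to accrue up to 144 patients (72 per arm) in order to collect an estimated 128 audio recordings (64 per arm".

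Only 13.3.4 states 72 per arm; in the other four places it follows from 144 and 1:1 allocation.

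**Accrual totals.** Section 4.1.2 says "a target of 315 patients will participate in the study" and lists the parts: 30 in Phase I, 168 in Phase II, 144 in Phase III, 24 in the exploratory focus groups and 5 in the cognitive interviews. The note under the accrual table in 4.1.1 gives up to 59 patients in Year 1 and 256 Fox Chase patients in Years 2-5, and then: "Overall, a lower accrual goal is 305, a total target accrual goal is 339, and an upper accrual goal for Fox Chase is 349". The provider target in 4.1.1 is 24.

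**The concern.** Randomising 144 patients 1:1 cannot put 64 in each arm. The 64 per arm in 4.3.3 matches the number of recordings that 13.3.4 hopes to obtain, so an analysable number appears to have been entered as a randomised number. Whoever builds the allocation list is likely to work from 4.3.3. If it is built for 128, the 128 recordings behind the power statements for outcomes 2A and 2B are reached only if every randomised patient yields one, and 13.3.4 does not expect that. The plan itself provides for visits that may go unrecorded: section 10.0 lets a clinician withdraw agreement to recording and stay in the study, and section 17.0 requires separate consent from a third party who is present.

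The accrual totals are a second, independent fault. The stated totals and the listed phase sizes cannot all be met, so the totals do not show how many patients Phases II and III are meant to contribute.

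**Working it through.** **1. The plan's own power figures (13.3.4).** Inputs: 64 recordings per arm; two-sided 5%; beliefs effect 0.5; outcome 2A 15% vs 38%; outcome 2B 22% vs 52%, with 70% of visits informative.

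- Beliefs, two-sample t-test (noncentral t): the required n is 63.8, rounded up to 64 per arm; power at 64 is 80.1%.
- 2A, full enumeration of the two-sided Fisher test at 64 per arm: 80.1%.
- 2B: 0.70 × 64 = 44.8, so 45 per arm; Fisher power 80.3%.

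All three of the plan's figures reproduce. The calculation is sound, and it rests on 64 *recordings* per arm.

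**2. The implied loss.** The plan gives no loss rate. From its two totals, 1 − 128/144 = 11.1%. Accruing 144 gives 144 × (128/144) = 128 recordings.

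**3. The effect of following 4.3.3.** Assume the same 11.1% loss applies to 128 randomised patients:

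- Recordings: 128 × 128/144 = 113.8, about 57 per arm.
- Informative for 2B: 0.70 × 57 = 39.9, about 40 per arm.

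| Outcome | As 13.3.4 intends | If 4.3.3 is followed, 11.1% loss |
|---|---|---|
| 2A, 15% vs 38% | 80.1% (64 per arm) | 75.2% (57 per arm) |
| 2B, 22% vs 52% | 80.3% (45 per arm) | 73.9% (40 per arm) |
| Beliefs, effect 0.5 | 80.1% (64 per arm) | 75.4% (57 per arm) |
| Beliefs, effect 0.60 | 92.0% (64 per arm) | 88.8% (57 per arm) |

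The intervention-arm rate detectable with 80% power rises from 38% to between 39% and 40% for 2A, and from 52% to about 54% for 2B. The beliefs outcomes come from surveys, and a missing recording need not remove the survey. Their power under 4.3.3 at an effect of 0.5 therefore lies between 75% (same loss as recordings) and 80% (all 64 per arm complete). With no loss at all, 4.3.3 costs no power.

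**4. Accrual totals.**

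| Quantity | Stated | From the listed parts | Gap |
|---|---|---|---|
| All patients (4.1.2) | 315 | 30 + 168 + 144 + 24 + 5 = 371 | 56 |
| Years 2-5 patients (4.1.1) | 256 | 168 + 144 = 312 | 56 |
| Patients and providers (4.1.1) | 339 | 371 + 24 = 395 | 56 |

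The stated totals agree with one another: 59 + 256 = 315 and 315 + 24 = 339. Year 1 agrees with its parts: 30 + 24 + 5 = 59. The 56 therefore lies in the combined Phase II and III count. As a share of the listed patients it is 56/371 = 15%. The other two goals do not show the same gap: 305 is 90 below 395, and 349, which is given for Fox Chase, is 46 below 395.

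**5. Are the two faults one?** Put 128 in place of 144: 30 + 168 + 128 + 24 + 5 = 355, still 40 above 315. They are separate.

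**6. Can the documents show which figure is out of date?** With Phase III at 144, the totals would need a Phase II of 256 − 144 = 112. The per-provider rule in 4.1.1 and 4.3.2 (6-8 providers, 8-16 visits at each of two periods) allows from 6 × 8 × 2 = 96 to 8 × 16 × 2 = 256. Both 112 and 168 lie inside that range, so the rule does not decide it.

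**The case against.** The strongest reply is that the document already settles the first point. Section 13.3.4 derives 144 and explains it, four other statements agree, and 4.3.3 is one sentence left uncorrected. Nothing makes 64 per arm a stopping rule: 13.3.4 ties accrual to obtaining 128 recordings, and 4.1.1 leaves the number of recorded visits open. The loss of power therefore needs two things to happen, accrual stopping at 128 and recordings then being lost at a rate the plan never states. Even then the detectable rates move by only about 2 percentage points, and beliefs, on which the sample size is based, keep 89% power at the assumed effect of 0.60. On accrual, Phase II has no sample size calculation and was not powered for formal comparisons, so the 56 is administrative. The text also calls some numbers approximate, and 256 is labelled as Fox Chase patients while outside sites are allowed.

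Much of this stands. The power figures are conditional, the effect is modest, and the weight of the text favours 144. It does not remove the contradiction, which sits in the section that defines the randomisation. The approximate wording covers no-shows and small shifts between sites, not 56 patients. The Fox Chase label does not explain the gap either, since 59 + 256 equals the all-patient 315 exactly. Nothing says that patients are counted in both phases. It is fair that the doubt over phase sizes falls mainly on Phase II or on outdated totals.

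**Conclusion.** Both inconsistencies are real.

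The number randomised in 4.3.3 (128) is 16 below the 144 given elsewhere, 8 per arm, and equals the expected number of recordings. If 4.3.3 were followed, and if recordings were lost at the inferred 11.1%, power would be about 75% for 2A and 74% for 2B instead of 80%, and 75% to 80% for beliefs at an effect of 0.5. If every randomised patient yielded a recording, nothing would be lost. The sample size calculation in 13.3.4 is correct and needs no change.

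The totals 315, 256 and 339 are each 56 below the parts listed. This is a matter of accrual planning with no shown effect on the Phase III inference, unless the lower totals reflect a smaller Phase III. The documents do not say which figure is out of date. The point should be fixed because the number randomised and the accrual target are figures the trial is run from.

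**What to change.** 1. In 4.3.3, state that 72 patients are assigned to each arm (144 in total), expected to yield about 64 recordings per arm. This agrees with 13.3.4 and changes no planned Phase III size.
2. Have the sponsor confirm the intended Phase II and Phase III sizes, then reconcile 4.1.1 and 4.1.2:
   - If 168 and 144 are intended, replace 315, 256 and 339 with 371, 312 and 395, and re-derive the lower goal (305) and the Fox Chase upper goal (349).
   - If the lower totals are intended, correct the phase sizes in 4.1.2. Should that reduce Phase III, restate its power in 13.3.4.

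The cost is a text amendment. The first item can be made at once; the second waits only on the sponsor's confirmation.
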